### **12.8.1 Corrective and preventive actions and principal disqualification criteria**

All CIP deviations will be documented and assessed. If required, corrective and preventive action will be agreed upon and implemented with the relevant site. These decisions, activities and possible preventive actions will be documented.

A Principal Investigator can be disqualified if he has repeatedly or deliberately failed to comply with the requirements as specified in the CIP, including compliance with the relevant regulations, or if he has submitted false information in any required report. Corrective actions may include supplemental protocol training, discussions with PI and study staff for activities to prevent future recurrence, etc.. Misconduct can cause PI disqualification.

### **12.9 Investigational device accountability**

The PCaVision investigational device will only be used on patients included in this study and following the study protocol.

The PCaVision device is SW running on an off the shelf computing unit (MacMini, Apple Inc.), the Computer Hardware will be labelled, including a serial number (See section 6.1) and will be installed by the staff of Angiogenesis Analytics on the clinical site. After the conclusion of patient inclusion at a specific clinical site the investigational device will be removed again.

Records will be kept of the identity (serial number) and location of each device as well as the data of installation and removal.

Due to the nature of the investigational device further device accountability (e.g. link to specific subject, expiry data and return of unused devices) is not appropriate.

## 13. STRUCTURED RISK ANALYSIS

A risk management plan, Policy template for Establishing Criteria for Safety Risk Acceptability, Risk Management Matrix, Risk Management Report and Benefit-Risk Determination have been created and approved. These documents are part of the Investigational Medical Device Dossier.

A summary overview of the risks and benefits of the investigational device and the clinical procedure applied in this clinical study are listed in the table below.

Anticipated clinical benefits	A potential benefit for the patients participating in this study when a clinically significant cancer is detected by targeted biopsies based on PCaVision that would otherwise have been missed by both MRI and systematic biopsies. Furthermore, the results of this study may be important for future patients suspected of prostate cancer. If PCaVision is sufficiently accurate, it could replace MRI as the central imaging strategy which would lead to a more streamlined and more cost-effective diagnostic work-up as the ultrasound examination is less costly and can be performed by urologists followed by targeted biopsies in the same session. If PCaVision is sufficiently sensitive, systematic biopsies after a negative ultrasound examination could even be omitted in the future, thereby reducing the burden associated with unnecessary biopsies.
Anticipated adverse device effects	There is a small, anticipated risk for participants (with a risk classification of negligible risk) associated with the administration of ultrasound contrast agent. However, adverse events caused by the ultrasound contrast agent appear to be transient, mild, and rare. These mostly consist of transient alteration of taste, local pain at the injection site and facial or general flush. In rare cases allergic reaction is described.
Residual risks associated with investigational device	In the risk analysis, in total 22 risks were identified of which 7 were classified as medium risks, and the other 15 as low risks. Of these 7 medium level risks, only 1 was not reduced to a low level after implementation of the risk mitigations. This risk involved an allergic response of the patient to the US contrast agent which could lead to an anaphylactic shock. In that situation, the standard of care protocol from the hospital should be followed to treat this anaphylactic shock. However, it is the responsibility of the clinic /hospital to act according to the standard of care in such situations.

Risks associated with participation in clinical study	Additional targeted biopsies could be performed because of the identification of PCa based on PCaVision imaging. These extra biopsies carry a small risk of haemorrhage and infection.
Possible interactions with concomitant medical treatments	There are no interactions with concomitant medical treatments
Steps that will be taken to control or mitigate risks	Risk are mitigated by specific mitigation actions as defined in the Risk Analysis File. For the 6 medium-level risks that were mitigated to low-level risk, adequate training and/or supervision of the operator, and detailed instructions in PCaVision 1.0's IFU were the most often mentioned mitigation actions.
Risk-to-benefit rationale	
The investigational device "PCaVision 1.0" has individual residual risks that are all acceptable and reduced as far as possible without introducing new risks or modifying the probability or severity levels of already defined risks.
 
During the clinical investigation, the patient will receive standard of care and there will be no diagnosis nor clinical decisions based on the output of PCaVision, the diagnosis is always based on the outcome of the biopsy results. Therefore, the investigational device will not contribute to any hazardous situation that could result in unacceptable risk after implementing risk control measures.
 
There could be a potential benefit for the patients participating in this study when a clinically significant cancer is detected by targeted biopsies based on PCaVision that would otherwise have been missed by both MRI and (potentially) systematic biopsies. However, even in the case where the patient do not receive immediate clinical benefit, the results of this study may be important for future patients suspected of prostate cancer. If PCaVision is sufficiently accurate, it could replace MRI as the central imaging strategy which would lead to a more streamlined and more cost-effective diagnostic work-up as the ultrasound examination is less costly and can be performed by urologists followed by targeted biopsies in the same session. If PCaVision is sufficiently sensitive, systematic biopsies after a negative ultrasound examination could even be omitted in the future, thereby reducing the burden associated with unnecessary biopsies.

None of the previous trials performing prostate imaging with CEUS reported procedure- or device-related adverse events. Apart from the aforementioned risks related to the

administration of contrast ultrasound there are no anticipated additional risks for participants in this study. The risk is negligible (“verwaarloosbaar risico”).

## **Appendix I**

### *Comparative analysis of the LOGIQ E10 R3 and LOGIQ E10 R4 ultrasound machines*

#### *Rationale*

This study compares the PCa detection rate based on MRI with that of ultrasound using PCaVision. PCaVision has been developed based on ultrasound images created with a GE LOGIQ E10 ultrasound device, version R3. A more recent iteration of the device (GE Logic E10, version R4) is available for use in patient care. To ensure that PCaVision operates safely with the input from this newer ultrasound device (R4), an in-patient comparison with both devices is necessary. New study patients who are willing to participate in the current study will be asked to undergo an additional scan with both devices.

#### *Procedure*

The procedure will be fully explained to the patient during the informed consent consultation. The patient will undergo two 10-minute scans in a single session. The ultrasound scans will be performed using a probe that is inserted transrectally only once. First, the R3 scan will be conducted, then the probe will be disconnected from the R3 device and connected to the R4 device. This way, the probe does not need to be reinserted in the rectum of the patient. In both scans, a bolus of contrast fluid (SonoVue) will be administered. There are no adverse effects associated with administering a second bolus, and it is described as safe by the manufacturer. The total procedure will take approximately 10 minutes longer than usual.

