### **7.2.2 Ultrasound contrast agent**

Sonovue® (sulphur hexafluoride, Bracco Imaging S.p.A., Colleretto Giacosa, Italy)

Information extracted from the European public assessment report (EPAR) for SonoVue (available from <http://www.ema.europa.eu/ema/>). The EPAR was last updated on 14/09/2021.

SonoVue is a medicine that contains the active substance sulphur hexafluoride (a gas). It is available as a kit including one vial of gas and powder and one prefilled syringe containing 5 ml of solvent. When made up into a solution, SonoVue contains sulphur hexafluoride gas as 'microbubbles' in suspension in a liquid. SonoVue is for diagnostic use only. It is a contrast agent (it helps make internal body structures visible during imaging tests). SonoVue is used in tests that measure how ultrasound travels within the body because it improves the ability of the blood to create an echo. The medicine can only be obtained with a prescription. SonoVue should only be used by doctors who have experience in diagnostic ultrasound imaging. It is injected intravenously (into a vein) before the test is carried out, as a 2- or 2.4-ml dose depending on which test is being carried out. The dose can be repeated. The active substance in SonoVue, sulphur hexafluoride, is a gas that is not soluble in the blood. When SonoVue is made up into a suspension, the gas is trapped in tiny bubbles called microbubbles. After injection, the microbubbles travel in the blood, where they reflect ultrasound waves more than the surrounding tissues. This helps to enhance the results of

tests that rely on measuring ultrasound, such as echocardiography and Doppler tests. The gas is removed naturally from the body through the lungs.

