#### *Ad 1. Intravenous administration of ultrasound contrast*

All patients will undergo 3D multiparametric ultrasound imaging before or during the targeted biopsy that is scheduled. To be able to carry out 3D multiparametric ultrasound, intravenous administration of an ultrasound contrast agent must be carried out. SonoVue® (sulphur hexafluoride, Bracco Imaging S.p.A., Colleretto Graciosa, Italy) will be used as the ultrasound contrast agent in this study. This is an additional procedure for patients participating in the study. In usual care, transrectal ultrasound examination is without contrast. SonoVue® is a registered product used in various ultrasound examinations of the heart, vasculature and of the excretory urinary tract. Details of this product and its usage can be found in Chapter 7.

In the procedure, an endorectal TRUS probe will be placed in the rectal cavity of the patient. Consecutively patients will undergo: 3D Doppler, 3D-SWE, 3D-B-mode and 4D-CEUS. For 4D-CEUS one 2.4mL bolus of SonoVue® will be administered intravenously. A two-minute recording in the contrast enhanced mode will be made following the administration of SonoVue®. The entire 3D mpUS imaging protocol will take approximately 10 minutes.

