#### *Analysis*

The primary and secondary analyses will be conducted using only the images obtained from the R3 device in order to ensure a uniform comparison between MRI and the R3 ultrasound images with PCaVision. A comparison of the R4 images with the R3 images will be conducted to ascertain whether software modifications are necessary to guarantee that PCaVision can be utilised with the R4 ultrasound system. The measured CEUS signal, SWE metrics and B-Mode will be compared. To validate the comparable output signals of R3 and R4, 50 patients will be required to undergo an additional R4 ultrasound scan.

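### Appendix I scans every man on R3 first and R4 second, so the R4−R3 difference measures device plus scan order and cannot by itself validate comparable output

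*Combined protocol and SAP*

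**What the plan says.** Appendix I (Procedure) sets one order for every man in the sub-study: "First, the R3 scan will be conducted, then the probe will be disconnected from the R3 device and connected to the R4 device". The probe stays in place. "The patient will undergo two 10-minute scans in a single session", and "In both scans, a bolus of contrast fluid (SonoVue) will be administered".

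Appendix I (Analysis) gives the aim and the sample size: "To validate the comparable output signals of R3 and R4, 50 patients will be required to undergo an additional R4 ultrasound scan". It names the signals: "The measured CEUS signal, SWE metrics and B-Mode will be compared". The result is meant to settle whether the software must be modified for R4. The same paragraph restricts the primary and secondary analyses to R3 images.

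Section 8.3.2 (Ad 1) gives the sequence within a scan: "Consecutively patients will undergo: 3D Doppler, 3D-SWE, 3D-B-mode and 4D-CEUS". The contrast recording comes last: "A two-minute recording in the contrast enhanced mode will be made following the administration of SonoVue". The whole imaging protocol is put at about 10 minutes.

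Appendix I mentions no alternating or randomised order, interval between scans, check for residual contrast, repeat R3 scan or order term. No other section supplies one.

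**The concern.** In a paired comparison of two devices, a fixed sequence makes device and scan position the same variable. A difference between R3 and R4 might come from being scanned second. Agreement might be a real device difference cancelled by an order effect in the other direction. Both possible decisions, to modify the software or to leave it alone, are exposed.

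An order effect is plausible. If R4 repeats the Section 8.3.2 sequence, its Doppler, shear-wave and B-mode images follow the R3 bolus, whereas R3's precede any contrast. Section 7.2.2 says that after injection "the microbubbles travel in the blood, where they reflect ultrasound waves more than the surrounding tissues". R4 also always follows roughly 10 minutes with the probe in place and a change of connection, when the patient may be moving more or less.

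The protocol accepts the principle elsewhere. Sections 5.1 and 8.2 randomise the order of the two targeted-biopsy procedures so that neither technique gains from always going first.

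**Working it through.** **The plan's own figure.** The 50 men cannot be reproduced. Appendix I gives no margin, standard deviation, error rate, power or analysis model. The question here is what the design can identify, so it does not depend on that number.

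**What the fixed order estimates.** Let δ be the device effect (R4 minus R3) and π the effect of being scanned second. For man *i*, the R4−R3 difference is *d*ᵢ = δ + π + *e*ᵢ. The mean over 50 men has expectation δ + π. Adding men shrinks the error around δ + π but never splits it.

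**Rank check.** A model with 50 patient effects, one device effect and one period effect has 52 columns.
- All 50 men R3 first: rank 51 of 52, so device and period are aliased.
- 25 R3 first and 25 R4 first: rank 52 of 52, so both can be estimated.

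**What balancing would and would not do.** Take second minus first scan. R3-first men have mean δ + π and R4-first men have mean −δ + π. Half the difference between the groups is [(δ + π) − (−δ + π)]/2 = δ, so a common order effect drops out. If carry-over differs by device, say λ₃ from R3 into R4 and λ₄ from R4 into R3, the same contrast gives δ + (λ₃ − λ₄)/2, and that part stays.

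**Precision.** 95% confidence interval half-widths, in units of the SD of the within-man difference:
- Fixed order: t(0.975; 49)/√50 = 0.284.
- 25/25 split: t(0.975; 48) × √(1/25 + 1/25)/2 = 0.284.

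**Illustration with assumed order shifts.** The documents give no order effect, so 0.25 and 0.5 SD are assumptions. Each row comes from 20,000 simulated trials of 50 men with a two-sided 5% t-test.

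| True device effect | Order shift | Significant, fixed order | Significant, 25/25 |
|---|---|---|---|
| 0 | 0 | 5.1% | 5.2% |
| 0 | 0.25 SD | 41% | 5.0% |
| 0 | 0.5 SD | 94% | 5.0% |
| 0.5 SD | 0 | 93% | 93% |
| 0.5 SD | −0.25 SD | 41% | 93% |
| 0.5 SD | −0.5 SD | 5.2% | 94% |

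With no order shift the two designs perform alike. The table shows how the conclusion depends on π; it is not evidence about the size of π.

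**Timing.** Assume that R4 repeats the Section 8.3.2 sequence and that the two-minute contrast recording closes each 10-minute scan. The R3 bolus then falls at about minute 10 − 2 = 8, and the R4 bolus at about minute 10 + 8 = 18 plus the time to reconnect the probe. The boluses are roughly 10 minutes apart, with R4's non-contrast modes between them. The documents give no clearance time for the agent, so residual contrast over that gap can be neither shown nor excluded.

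**The case against.** The best defence is that R3 first is a sensible choice. The R3 scan feeds the confirmatory comparison and determines the PCaVision biopsy targets. Scanning it first keeps every primary scan free of a prior bolus and of prior probe time. The plan does not give this reason, but it stands.

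The defence can also say that carry-over may be small. Section 7.2.2 says the dose can be repeated and that the gas leaves through the lungs. Section 6.2.1 describes the older 2D technique as needing a bolus and five minutes for each imaging plane, so closely spaced boluses are not new. None of this gives a clearance time or shows that the second scan is unaffected, but it does rule out treating residual contrast as established.

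A reader might infer four stronger things that the documents do not support:
- **That all three compared signals are distorted.** Section 7.2.2 describes stronger echoes from blood. Nothing says that shear-wave metrics or B-mode are altered by residual contrast.
- **That the quality thresholds give the size of the problem.** In Section 6.1.2 the loose and strict limits differ by 50 − 43 = 7 dB and 8.1 − 3.0 = 5.1 mm. These are gaps between quality gates, not order effects or agreement margins.
- **That the comparison is worthless.** Close agreement would support comparability if the order effect were known to be negligible. What is missing is any statement or check of that condition.
- **That scan order must be randomised.** This would put the primary R3 scan second in about 25 men, 25/438 = 5.7% of the planned total. Under Sections 6.1.2 and 10, a scan failing the quality check is not processed and the man leaves the paired dataset. A sensitivity analysis omitting the R4-first men cannot bring him back.

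**Conclusion.** The point holds within the sub-study. Under the stated sequence, device and order are completely aliased in 50 of 50 men, so the aim of validating comparable output does not follow from the design without an unstated and untested assumption of no order effect. That aliasing rests only on the sequence in Appendix I. The contrast mechanism rests further on R4 repeating the Section 8.3.2 sequence, which Appendix I implies through its two 10-minute scans but does not spell out.

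The size of any order effect is unknown, and the percentages in the table depend on assumed shifts. A reader might also infer that the main trial result is compromised. It is not, because the primary and secondary analyses use R3 images only and R3 comes first. What is at stake is the later decision on using PCaVision with R4.

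**What to change.** Keep R3 first, and amend the Analysis text of Appendix I along these lines: *R4 images are acquired as a second scan, after the R3 scan and its contrast bolus. The R4−R3 difference estimates the device difference together with any effect of scan order, and will be reported as such. It will not be taken as validation of comparable output, nor be the sole basis for deciding that no software modification is needed.*

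In all 50 men, record the time between boluses. Where the contrast-mode recording already captures it, also record the contrast intensity before the second bolus arrives. Report the R4−R3 differences against both. A trend would point to carry-over. A flat pattern would be reassuring, but it could not exclude an order effect that is constant across men, so the narrower wording is still needed. No dose or interval is proposed here.

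Randomising scan order 1:1, with the computer-generated list method already used for the biopsies, remains an option for the sponsor. It would separate a common order effect from device with no loss of precision. Against that stand the risk to about 25 primary scans and the device-specific carry-over that it would leave in place.

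The cost of the main change is a short amendment, a narrower stated conclusion and minor extra data recording. It needs no extra scans, boluses or men.

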The most common side effects with SonoVue (seen in between 1 in 100 and 1 in 1,000 patients) are headache, paraesthesia (unusual sensations like pins and needles), dizziness, dysgeusia (taste disturbances), flushing (reddening of the skin), pharyngitis (sore throat), nausea (feeling sick), abdominal pain, pruritus (itching), rash, back pain, chest discomfort, reactions at the injection site, feeling hot and raised blood sugar levels. For the full list of all side effects reported with SonoVue, see the package leaflet. SonoVue must not be used in patients known to have right-to-left shunts (abnormal movement of blood within the heart), severe pulmonary hypertension (high blood pressure in the pulmonary artery, the blood vessel that leads from the heart to the lungs), uncontrolled hypertension (high blood pressure) or adult respiratory distress syndrome (severe fluid build-up in both lungs). SonoVue must also not be used together with the medicine dobutamine (used for heart failure) in patients for whom dobutamine is not suitable. For the full list of restrictions, see the package leaflet. The CHMP decided that SonoVue's benefits are greater than its risks and recommended that it be given marketing authorisation. The European Commission granted a marketing authorisation valid throughout the European Union for SonoVue on 26 March 2001.

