### **7.4. Preparation and labelling of Non-Investigational Medicinal Product - ultrasound contrast agent**

#### **7.4.1 Preparation**

Pack size: 1 vial + 1 pre-filled syringe + 1 'MiniSpike' rec. device

If SonoVue is not used immediately after reconstitution the dispersion will be shaken again before being drawn up into a syringe. The product is for a single examination only. Any unused liquid remaining at the end of an examination must be discarded.

[figure not shown]

Figure 3: Reconstitution instructions

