## **9. SAFETY REPORTING**

### **9.1. Ultrasound and ultrasound contrast agent**

Ultrasound is considered a safe diagnostic tool because of the use of non-ionizing radiation. In general, few side-effects are attributed to ultrasound microbubble contrast agents. Complications like nephrotoxicity, which can occur with iodine containing contrast media in use for CT, have never been reported. Adverse events of microbubble contrast media appear to be transient, mild and rare [38,39,40]. The most frequently mentioned minor side-effects of microbubble contrast agents are transient alteration of taste, local pain at the injection site and facial or general flush (1-5%) [41]. Serious adverse events, which consists of hypersensitivity allergic reactions, are rare (<0.01%) [42]. Because the gaseous content of the microbubble agents is eliminated by the lungs, it is of importance to evaluate whether impaired pulmonary function could be a contraindication for the use of microbubbles. In a study with SonoVue® (Bracco, Geneva) in patients with Chronic Obstructive Pulmonary Disease, CEUS appeared to be as safe and well tolerated as in a healthy control group [38]. The Committee for Medicinal Products for Human Use (CHMP) has granted SonoVue® a marketing authorization, but it should not be used together with the medicine dobutamine and in pregnant or breastfeeding women ([www.emea.eu](http://www.emea.eu)).

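### Appendix I says a second SonoVue bolus is free of adverse effects, contradicting the protocol's own contrast risk statements, and the benefit-risk sections omit the 50 men who receive two boluses

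*Combined protocol and SAP*

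**What the plan says.** Appendix I (Procedure) describes an R3 scan followed by an R4 scan in one session, with the probe inserted once. On contrast it says: "In both scans, a bolus of contrast fluid (SonoVue) will be administered". On safety it says: "There are no adverse effects associated with administering a second bolus, and it is described as safe by the manufacturer". It gives no reference for this and no volume for the second bolus. Appendix I (Analysis) sets the number: "50 patients will be required to undergo an additional R4 ultrasound scan". Section 8.3.2 (Ad 3) gives the same number and points to the appendix.

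The contrast risk is described elsewhere as follows.

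- Section 7.2.2, from the European public assessment report: "The most common side effects with SonoVue (seen in between 1 in 100 and 1 in 1,000 patients"), followed by a list of effects.
- Section 9.1, for microbubble agents as a class: "transient alteration of taste, local pain at the injection site and facial or general flush (1-5" per cent), with serious hypersensitivity put below 0.01%.
- Section 11.3: the same minor effects, plus allergic reaction in rare cases.
- Chapter 13, on the only one of seven medium risks not lowered by mitigation: "This risk involved an allergic response of the patient to the US contrast agent which could lead to an anaphylactic shock".

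On dosing, section 8.3.2 (Ad 1) says: "For 4D-CEUS one 2.4mL bolus of SonoVue® will be administered intravenously". Section 7.3.1 gives 2.4 mL and does not mention a repeat. Section 7.4.1 says: "The product is for a single examination only". Section 7.2.2 notes that the dose may be repeated. Section 7.1.2 states that the use in this study is off-label.

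**The concern.** The Appendix I sentence is absolute. It does not say that a repeat adds little risk, or that no further effects are known. It says there are none, about an agent for which the same protocol lists common minor effects and one residual medium-level risk. Permission to repeat a dose, as in section 7.2.2, does not show that the repeat is without effects.

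The sections that weigh burden and risk (the burden and risk part of the Summary, section 11.3 and chapter 13) do not mention that some men are exposed twice. For those men the only statement on the risk of the added off-label exposure is the one in Appendix I. An ethics committee, or a site preparing its explanation for patients, would read it there. What is at stake is the accuracy of the safety text, not any efficacy result.

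**Working it through.** **Consistency of the safety statements.** The documents give no adverse-event rate for a second bolus, and the number 50 has no stated derivation, so there is no plan figure to reproduce. The statements can be set side by side:

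| Place | Statement about SonoVue or its class |
|---|---|
| Appendix I, Procedure | no adverse effects from a second bolus |
| 7.2.2 | most common effects in 0.1% to 1% of patients |
| 9.1 | minor effects 1% to 5%; serious hypersensitivity below 0.01% |
| 11.3 | minor effects, and allergic reaction in rare cases |
| 13 | allergic response, possibly anaphylactic shock, still at medium level after mitigation |

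No section says that these risks vanish on re-exposure. The first row cannot stand beside the other four as written.

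**Size.** Assumption: each rate applies per bolus, and equally to a second bolus. With n = 50, the expected number of men reacting to the second bolus is 50 × p, and the chance of at least one is 1 − (1 − p)^50.

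| p | Source | Expected men, 50 × p | Chance of at least one |
|---|---|---|---|
| 0.01% | 9.1, ceiling for serious reactions | 0.005 | 1 − 0.9999^50 = 0.5% |
| 0.1% | 7.2.2, lower end | 0.05 | 1 − 0.999^50 = 4.9% |
| 1% | 7.2.2 upper end; 9.1 lower end | 0.5 | 1 − 0.99^50 = 39.5% |
| 5% | 9.1, upper end | 2.5 | 1 − 0.95^50 = 92.3% |

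Minor reactions therefore range from unlikely to nearly certain, depending on which of the protocol's rates is used. A serious reaction among 50 men is very unlikely on any of them.

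The substudy could not establish absence of effects either. With zero events in 50 men, the one-sided 95% upper bound is 1 − 0.05^(1/50) = 5.8%, above every rate in the table.

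**Dosing text.** Section 8.3.2 (Ad 1) describes one bolus of 2.4 mL, whereas Appendix I gives one in each of two scans. Section 8.3.2 (Ad 3) announces the extra scan but mentions neither a second bolus nor its volume. Section 7.4.1 limits the product to one examination, and Appendix I does not say whether two scans in one session count as one. These passages need reconciling.

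**Adverse-event recording.** Section 9.3.1 records all events that are reported or observed, in all men. No section separates events by number of boluses.

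**The case against.** The sentence may have been meant as no *additional* adverse effects. Chapter 13 closes by saying that earlier prostate CEUS trials reported no procedure- or device-related events, section 6.2.1 notes that 2D CEUS needs a bolus for each plane, and the manufacturer's statement is not available to check. That may well be the intention, but the text does not say so. The closing remark in chapter 13 also sets the contrast risks apart before declaring that no further risks are expected.

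The rates are not second-bolus rates. Section 7.2.2 counts patients, and section 9.1 covers the agent class. This stands: the counts above illustrate size under an assumption and are not estimates. The contradiction itself does not depend on them.

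Four stronger readings are tempting, and the documents do not support them.

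- *The 50 men are misinformed.* The consent pages are not in the review copy. Section 11.3 says patients will be told of the contrast risk, and Appendix I promises a full explanation of the procedure.
- *Double exposure is not tracked.* Section 9.3.1 covers events in all men, section 12.2 gives monitoring an extra focus on contrast use, and two-bolus men can be identified by their R4 scan. The content of the eCRF is not in the documents.
- *The dosing sections flatly contradict Appendix I.* Section 8.3.2 itself cross-refers to the appendix, and section 7.2.2 allows a repeat. What remains is an incomplete reconciliation.
- *Vial handling biases the R3 versus R4 comparison.* Nothing shows that sites would differ in vial use or that this would change the signal.

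**Conclusion.** The Appendix I sentence is wrong as written. It conflicts with sections 7.2.2, 9.1, 11.3 and chapter 13, and the benefit-risk text omits the two-bolus exposure of 50 men. This conclusion rests on the wording alone.

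Its size rests on the assumption that the protocol's rates apply per bolus: about 0.05 to 2.5 men with a reaction to the second bolus, and about 0.005 with a serious one at the stated ceiling. The practical risk is small, but it is not nil.

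The point is confined to safety text and internal consistency. Appendix I restricts the primary and secondary analyses to R3 images, and the R3 scan comes first, so no trial endpoint is affected.

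**What to change.** 1. Delete the sentence on adverse effects from Appendix I and refer instead to the contrast risks in sections 7.2.2, 9.1 and 13.
2. Update section 11.3 and chapter 13 to say that 50 men receive two boluses, and bring the burden and risk text of the Summary into line.
3. Check the patient information for the same wording and correct it if it is there.
4. The sponsor should reconcile sections 7.3.1, 7.4.1 and 8.3.2 with Appendix I on the second bolus, including its volume and whether the two scans count as one examination. No view is taken here on which dosing is right.
5. Optionally, list adverse events for the two-bolus men separately. With so few events expected, this would be description only, with no comparison or test.

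The cost is a few sentences and, if wanted, one extra listing. The number of men, the scans and the analyses do not change. The one drawback is that the stated risk becomes slightly less favourable.
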